Second intercostal space parasternal EMG, acquired using electrodes placed on the chest wall on either side of the sternum, avoids this technical difficulty. The parasternal muscles are obligate muscles of respiration with minimal post-inspiratory activity. Furthermore, the parasternal muscles make a relatively greater contribution to ventilation during periods of increased hyperinflation, such as during an acute exacerbation of COPD (AECOPD), as the resting length of the parasternal muscles is less affected than diaphragm^21. The activity of these muscles would be expected to be high at the beginning of an AECOPD and decrease with subsequent unloading of the parasternal muscles through treatment with bronchodilators, corticosteroids and antibiotics.

In a pilot feasibility study of this technique, Murphy *et. al.* demonstrated that the change in NRD during hospital admission was a marker of physician-defined clinical deterioration and, furthermore,

change in NRD from admission to discharge identified patients with COPD who were readmitted within 14 days. This study was in a small group of selected patients with AECOPD, with the majority of patients having only a single pair of NRD measurements made during their hospital admission. The NRD was derived from the RMS of the parasternal EMG expressed as a percentage of maximal parasternal EMG obtained during a sniff manoeuvre ( $EMG_{para\%max}$ ). An additional clinically useful measure was the NRD index (NRDI), which was calculated as the product of  $EMG_{para\%max}$  and respiratory rate.

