#### Pre-discharge measurements

The investigator will perform a final study visit on the day of discharge collecting the following data:

- Medications (acute & chronic)
- Up to date venous blood tests (haemoglobin, white cell count including differential, platelet count, urea, creatinine, C-reactive protein) and arterial blood gas if performed by the clinical team. These tests do not need to be performed by the research team.
- Vital observations
- COPD assessment test (CAT)
- EXACT-PRO questionnaire
- Spirometry – FEV1, FVC, IC
- NRD
- Participants will be issued with a wrist-worn physical activity monitor which should be worn for the remaining duration of the study, apart from short periods for personal hygiene

**Home measurements** to be collected by the investigator:

- EXACT-PRO
- Neural respiratory drive (resting and maximal manoeuvres)
- Review of participants' symptom diaries
- COPD assessment test (CAT) (weekly)
- Spirometry – FEV1, FVC, IC (weekly)
- Physical activity monitors will be collected at the final assessment

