These 3 modalities (EMGpara, pressure-based respiratory signal and accelerometer) are connected to the automated EMG analysis system. This system is based on the Porti device from the TMSi company. The Porti system is CE certified (class 2A, type CF) and FDA 510k approved. The automated EMG analysis system extends the Porti device by providing bespoke software to capture, visualize and process the received data. The software runs on a laptop computer connected by USB cable to the fibre/USB interface of the Porti. Data is processed by the software to identify the inspiratory portion of the EMG signal and calculate an index of neural respiratory drive, as reported previously (EMGpara in microvolts (µV), EMGpara%max as the ratio to the maximum sniff EMGpara (by instructing the patient to undertake three maximal sniffs) and NRD (product of EMGpara%max and respiratory rate). The processed data (i.e. the indices of NRD) are not displayed online and not provided to the investigator. It therefore cannot influence clinical judgment. The software as tested in the study does not deliver any diagnosis, prevention, monitoring, treatment or alleviation of disease.

Before starting any spot-check NRD measurement, it will be ensured that the participant is seated in a relaxed semi-recumbent position with posture to ensure minimal tonic activity of anterior chest wall muscles. This practically entails participants to be seated with arms supported by arm rests or a pillow on the lap. The process of measuring NRD indices is expected to take approximately 10 minutes. To obtain the measurements of NRD, raw EMGpara, RMS EMGpara and airflow will be obtained over a seven minute 'spot check' period. In the final minute, patients will be asked to perform a minimum of six maximal sniff manoeuvres in order to obtain maximal sniff measurements. This data will be analysed after data acquisition using an automated algorithm to obtain NRD and sniff measurements.

NRD measurements will be recorded by an investigator during participants' hospital stay following the procedure described above. Measurements will be taken twice daily, one pre-SABD and the second

20-minute post-SABD. The timing of NRD measurements should stay consistent throughout their hospital admission.

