#### **9.4 Follow up Procedures**

##### **Hospital Discharge and subsequent readings**

On the day of discharge, vital observations, spirometry (FEV1, FVC, IC) and NRD will be measured and the EXACT-PRO and CAT symptom questionnaires will be completed. The list of discharge medications will be documented. Patients will be issued with physical activity watches on the day of discharge and this should be worn for the remaining duration of the study, apart from short periods for personal hygiene.

The study staff will schedule a time to visit the participant the next day after their discharge. The timing of the visit will be scheduled at the participant's convenience however should remain the same time for the remaining duration of the study. At each visit, the EXACT-PRO questionnaire will be completed and EMG measurements performed. NRD will be analysed after the home visit is completed. A symptom dairy will be recorded along with record of additional medications used which will be reviewed by the investigator. The CAT questionnaire and spirometry (FEV1, FVC, IC) will be performed weekly at home.

If, when during conducting the measurements in the home setting, the assessment of the investigator is that the patient has a significant exacerbation and requires emergency treatment they will use the following traffic light system to provide assistance:

- Green: The participant is clinically stable with an increase in their COPD symptoms – the investigator will signpost the participant to take the course of action they usually would (for example using their rescue pack and/or arranging an appointment with their General Practitioner).
- Amber: The participant is more unwell than category Green but less unwell than category Red – the investigator will signpost the participant to take the course of action they usually would and additionally provide an escalation plan to seek urgent medical attention should they deteriorate (GP appointment or attendance at their local Accident and Emergency department).
- Red: The participant is critically unwell – Investigator will urgently call 999 to request an ambulance.

If the patient requests a medical review the investigator will direct the patient to the usual health care provider for the patient.

The final study visit at day 30 will ensure completion of questionnaires, collection of physical activity monitors and confirmation of health status.

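### Home NRD readings are held to clock time but not to bronchodilator state, so the hospital-to-home change sets a controlled state against an uncontrolled one, and the primary endpoint may do the same

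*Protocol*

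**What the plan says.** **In hospital.** Section 9.3 (NRD measurement) defines two bronchodilator states each day: "Measurements will be taken twice daily, one pre-SABD and the second" "20-minute post-SABD. The timing of NRD measurements should stay consistent throughout their hospital admission". The opening of that paragraph limits the rule to the admission: "NRD measurements will be recorded by an investigator during participants' hospital stay following the procedure described above".

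**At home.** The home list in section 9.3 asks for "Neural respiratory drive (resting and maximal manoeuvres" and attaches no SABD condition. Section 9.4 lets the visit time suit the participant but says it "should remain the same time for the remaining duration of the study". Section 13.1 repeats the home visits without adding a bronchodilator rule. Medication is tracked in section 9.4: "A symptom dairy will be recorded along with record of additional medications used". Section 12.1 makes the diary daily.

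**Endpoints (section 7.1).** The primary endpoint is the change in NRD from a baseline to the day before an exacerbation. One secondary endpoint is the change from the hospital peak to the recovery baseline at home.

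**Premise (section 5).** Parasternal activity is expected to be high at the start of an exacerbation and then to "decrease with subsequent unloading of the parasternal muscles through treatment with bronchodilators, corticosteroids and antibiotics".

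**The concern.** A constant clock time does not give a constant interval since the last dose of a drug that may be taken as needed. Two home readings at the same hour can fall before a dose on one day and soon after it on another. In hospital the protocol removes this variation by design. At home it neither removes it nor, as written, captures it.

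Two endpoints are at stake. The hospital-to-home change crosses the two settings directly. The primary endpoint normally ends on a home reading, so its exposure depends on where its baseline was taken. An SAP can choose comparators and models, but it cannot recover dose times that were never collected. The point therefore belongs with the protocol's measurement procedure. The study's data are also meant to size later work (section 14.1), so an avoidable shift in NRD change would carry forward.

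**Working it through.** The protocol states no figure to reproduce. The check sets the two procedures side by side and then expresses the consequence in symbols.

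**Comparison**

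| | Hospital (9.3) | Home (9.3, 9.4, 13.1) |
|---|---|---|
| SABD state | Pre-dose, and 20 minutes post-dose | Not specified |
| Timing rule | Consistent during the admission | Same clock time each visit |
| Time of last dose | Implied by the schedule | No stated requirement |

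**Notation.** Let d be the fall in NRD at 20 minutes after SABD. Let q be the share of home readings taken under that effect. Neither is given in the protocol. For simplicity each home reading is treated as either fully pre-dose or fully post-dose. Bias is measured against a pre-dose-to-pre-dose change, with change = home minus hospital.

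**Hospital to home**
- Hospital value pre-dose: bias = −d × q.
- Hospital value post-dose: bias = −d × q + d = d × (1 − q).
- Difference between the two choices: d × (1 − q) − (−d × q) = d, whatever q is.

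Illustration, assuming d = 2 to 6 EMGpara%max points and q = 0.5:
- Pre-dose comparator: −2 × 0.5 = −1 to −6 × 0.5 = −3 points. Recovery looks larger than it is.
- Post-dose comparator: +2 × 0.5 = +1 to +6 × 0.5 = +3 points. Recovery looks smaller than it is.
- Gap between the two: 2 to 6 points.

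**Primary endpoint, hospital baseline.** The same formulas apply.

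**Primary endpoint, home baseline.** Let q0 be the share at baseline and q1 the share on the day before onset. Bias = −d × (q1 − q0).
- If q1 = q0, the bias is 0 on average and only noise is added.
- If q rises from 0.3 to 0.7 (assumed), the bias is −2 × 0.4 = −0.8 to −6 × 0.4 = −2.4 points, which would tend to hide a true rise.

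These values show direction and structure. They do not estimate what will happen in this study.

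**The case against.** A reader might infer that both endpoints are confounded and that the primary analysis is biased towards missing the signal. The documents do not support that.

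- **The primary endpoint may be like for like.** With a home baseline, both readings follow the same rule, and bias needs a rise in post-dose readings before onset. The protocol does not say that this happens. Section 5 lists greater beta-agonist use among the physician's treatment escalations, so it is part of the event, whereas the endpoint uses the day before. A rise is plausible if an event is dated by treatment or admission after symptoms have already begun, but it is not shown.
- **The Introduction does not isolate a dose effect.** Its sentence covers bronchodilators, corticosteroids and antibiotics together over the course of an exacerbation. The paired hospital readings show that the investigators consider SABD state worth measuring, not that the effect is large.
- **The hospital pairs are a partial safeguard.** They allow each patient's SABD effect to be estimated, and an SAP that is not shown may name the comparator.
- **Medication is already logged.** The diary and CRF layouts are not shown, so dose times may in practice be written down.
- **Routine adjustment could do harm.** SABD use may itself mark deterioration, so adjusting for it could remove part of the signal. Events will also be few: section 11 expects about 20% to be readmitted, or 0.20 × 30 = 6 readmissions, although exacerbations managed without admission would add to that.

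The first, second and last objections stand and limit the claim. The third and fourth only soften it. Knowing a patient's hospital dose effect does not reveal the state of a home reading. The log of extra medication carries no stated requirement for the time of the last SABD before each NRD reading, and regular doses may not count as extra.

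**Conclusion.** The mismatch is real on the text. Hospital readings have a defined bronchodilator state and home readings do not. For the hospital-to-home secondary endpoint this follows directly from the procedures as written, and the result depends on the hospital reading chosen by the full SABD effect, d. For the primary endpoint the conclusion is conditional. It is exposed in the same way with a hospital baseline. With a home baseline it is biased only if SABD use near the visit rises before onset, and then in the direction of hiding a rise.

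The size is unknown. The figures of 2 to 6 points for the secondary endpoint, and 0 to −2.4 points for a home-based primary endpoint, rest wholly on assumed values of d and q and on treating each home reading as one of two states. In an unpowered observational pilot of 30 patients, this is a cheap improvement to data collection. It does not show that the study's findings would be invalid.

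**What to change.** 1. At every home NRD reading, record the time of the last SABD dose, extending the medication record already kept under section 9.4.
2. State which hospital reading, pre- or post-SABD, is the comparator for the hospital-to-home change, and for the primary endpoint if its baseline is a hospital value. Compare it with home readings in the closest matching state.
3. Reconcile the NRD measurement text in section 9.3 with the home procedures in section 9.4, so that the handling of SABD state is explicit in both settings.
4. Use time since SABD in a sensitivity analysis, reporting results with and without it, and not as a routine covariate.

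The cost is one CRF field at a visit the investigator already makes, plus one extra analysis. Self-reported dose times are imperfect, and some home readings, for example those taken hours after a dose, will match neither hospital state. The change concerns recording and comparison only and implies no change to patients' medication.

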#### **9.4 Follow up Procedures**

##### **Hospital Discharge and subsequent readings**

On the day of discharge, vital observations, spirometry (FEV1, FVC, IC) and NRD will be measured and the EXACT-PRO and CAT symptom questionnaires will be completed. The list of discharge medications will be documented. Patients will be issued with physical activity watches on the day of discharge and this should be worn for the remaining duration of the study, apart from short periods for personal hygiene.

The study staff will schedule a time to visit the participant the next day after their discharge. The timing of the visit will be scheduled at the participant's convenience however should remain the same time for the remaining duration of the study. At each visit, the EXACT-PRO questionnaire will be completed and EMG measurements performed. NRD will be analysed after the home visit is completed. A symptom dairy will be recorded along with record of additional medications used which will be reviewed by the investigator. The CAT questionnaire and spirometry (FEV1, FVC, IC) will be performed weekly at home.

If, when during conducting the measurements in the home setting, the assessment of the investigator is that the patient has a significant exacerbation and requires emergency treatment they will use the following traffic light system to provide assistance:

- Green: The participant is clinically stable with an increase in their COPD symptoms – the investigator will signpost the participant to take the course of action they usually would (for example using their rescue pack and/or arranging an appointment with their General Practitioner).
- Amber: The participant is more unwell than category Green but less unwell than category Red – the investigator will signpost the participant to take the course of action they usually would and additionally provide an escalation plan to seek urgent medical attention should they deteriorate (GP appointment or attendance at their local Accident and Emergency department).
- Red: The participant is critically unwell – Investigator will urgently call 999 to request an ambulance.

If the patient requests a medical review the investigator will direct the patient to the usual health care provider for the patient.

The final study visit at day 30 will ensure completion of questionnaires, collection of physical activity monitors and confirmation of health status.

##### **Medical record review**

The study investigator will corroborate patient reported events with primary care physicians and local hospital electronic patient records to confirm nature and timings of visits.

#### **9.5 Radiology Assessments**

If participants' have had a chest radiograph on admission to hospital, this will be reviewed by the investigator at the baseline assessment for the presence of focal consolidation.

#### **9.6 End of Study Definition**

The trial will cease when the final patient has completed 30 days of home monitoring or has an exacerbation requiring hospital re-admission or 12 months from trial initiation, whichever is sooner.

## 10 Laboratories

### 10.1 Central/Local Laboratories

The research group is based at the Lane Fox Unit, St Thomas' Hospital. NRD will be analysed using bespoke computer software using data derived from EMG measurements.

### 10.2 Sample Collection/Labelling/Logging

All measurements are de-identified when entered into research software. Patient study identifiers will be used. The results of blood samples included in this study are taken as part of routine clinical care. No blood tests beyond routine care will be taken by investigators.

### 10.3 Sample Analysis Procedures

EMG measurements are analysed by research software to generate a measurement of NRD.

### 10.4 Sample Storage Procedures

Not applicable.

### 10.5 Data Recording/Reporting

Source documents are original documents, data, and records from which participants' CRF data are obtained. CRF entries will be considered source data. In this study the CRF will be used as the source document for all participants recruited into the study.

All documents will be stored safely in confidential conditions. On all study-specific documents, other than the signed consent, the participant will be referred to by the study participant number/code, not by name.

### 10.6 Sample Receipt/Chain of Custody/Accountability

Not applicable

### 10.7 Sample Transfer to sites outside the Organisation

Not applicable

## 11 Assessment of Safety

### Adverse event (AE)

An AE or adverse event is any untoward medical occurrence in a participant or other clinical investigation whilst participants are taking part in the trial; which does not necessarily have to have a causal relationship with the assessment being undertaken.

An AE can therefore be any unfavourable and unintended sign (including an abnormal laboratory finding), symptom or disease temporally associated with the assessment, whether or not considered related to the study.

### Serious adverse event (SAE)

SAE is an adverse event that

- Led to death
- Led to serious deterioration in the health of the subject that
- Resulted in a life-threatening illness or injury

Note: The term "life-threatening" in the definition of "serious" refers to an event in which the participant was at risk of death at the time of the event; it does not refer to an event which hypothetically might have caused death if it were more severe.

- Resulted in a permanent impairment of a body structure or a body function
- Required in-patient hospitalisation or prolongation of existing hospitalisation
- Resulted in medical or surgical intervention to prevent permanent impairment to a body structure or a body function
- Other important medical events\*

\*Other events that may not result in death, are not life threatening, or do not require hospitalisation, may be considered a serious adverse event when, based upon appropriate medical judgement, the event may jeopardise the patient and may require medical or surgical intervention to prevent one of the outcomes listed above.

To ensure no confusion or misunderstanding of the difference between the terms "serious" and "severe", which are not synonymous, the following note of clarification is provided:

The term "severe" is often used to describe the intensity (severity) of a specific event (as in mild, moderate, or severe myocardial infarction); the event itself, however, may be of relatively minor medical significance (such as severe headache). This is not the same as "serious," which is based on patient/event outcome or action criteria usually associated with events that pose a threat to a participant's life or functioning. Seriousness (not severity) serves as a guide for defining regulatory reporting obligations.

In addition, a serious AE is one that is judged by the investigator to be an important or medically significant event. Causality assessments of AEs: For all AEs, the investigator will provide an assessment of causal relationship to study devices. Appropriate forms will be used for this purpose and filed in the case report forms and submitted to the IRB for review. They will be classified as related, possibly related, and not related. The severity will be adjudged as being mild, moderate, or severe. All significant adverse events will be reported to the Institutional Review Board within 24 hours.

AECOPD is a clinical diagnosis made when a patient with COPD experiences a sustained (e.g. 24–48 h) increase in cough, sputum production, and/or dyspnoea. It commonly occurs in the cohort of patients under investigation in this study, who are at high risk of developing an AECOPD and indeed 20% will be readmitted to hospital within 28 of being discharged (when the primary reason for admission was AECOPD). The Chief Investigator and Principal Investigator therefore deem AECOPD to be an expected AE and SAE and AECOPD will not be reported to the sponsor. In the event of a participant developing an AECOPD, this will be documented in the participant's medical notes and case record file.

### Reporting of AEs

All AE's occurring during the study observed by the investigator or reported by the participant, whether or not attributed to the assessments being made will be recorded on the CRF as specified in the protocol. The following information will be recorded: description, date of onset and end date, severity, assessment of relatedness to assessments and/or intervention, action taken and information should be provided as necessary.

